#### 3.2.8.2 Laboratory Variables

Local laboratory results will only be listed.

Central laboratory results will be summarized with descriptive statistics at each scheduled time and for the change from baseline. Repeated or unscheduled tests will not be summarized for each scheduled visit (with the exception of baseline which may include unscheduled visits). Baseline values and values at each visit for each laboratory parameter collected be descriptively summarized and plotted over time using a boxplot.

Laboratory data will also be summarized using shift tables where appropriate. Each patient's continuous laboratory safety parameter values will be flagged as "low", "normal", "high" or "missing" relative to the normal ranges. Each patient's categorical laboratory safety parameter values will be flagged as "abnormal" or "normal". This categorical data will be summarized in shift tables comparing the minimum post-baseline value, maximum post-baseline value and all other relevant post-baseline visits with those at the baseline visit. Note that minimum post-baseline will only be displayed in the instances where there is a range with lower limit of normal (LLN) >0. For parameters that have gradings for both low and high values, low and high will be summarized separately.

In the shifts of low values, any high values will be classified as normal and the worst low grade will be summarized. And in the shifts of high values, any low values will be classified as normal and the worst high grade will be summarized.

In addition, CTCAE grade and hyperphosphatemia grade will be summarized. Shift tables of grade from baseline to maximum or minimum on-treatment as applicable will be produced.

Since hyperphosphatemia is not defined by CTCAE v. 4.03, as per protocol hyperphosphatemia is defined as:

Grade 1: > upper limit of normal (ULN) to < 7.0 mg/dL (<2.26 mmol/L)

Grade 2: Non-invasive intervention required (e.g., withhold drug or modify dose) or between 7.0 - 9.0 mg/dL (2.26 - 2.90 mmol/L)

Grade 3: Severe or medically significant, but not immediately life threatening, or > 9.0 - 10.0 mg/dL (> 2.90 - 3.23 mmol/L)

Grade 4: Life-threatening consequences, urgent intervention indicated e.g., dialysis, or > 10.0 mg/dL (> 3.23 mmol/L)

Central and local laboratory results will be included in by-patient listings and will include CTCAE grade and hyperphosphatemia grade at each visit, as well as change from baseline at each visit.

# Hy's law

Patients who have elevated alanine aminotransferase (ALT), aspartate aminotransferase (AST), and total bilirubin post baseline will be summarized descriptively as follows and Hy's law cases identified.

- ALT and AST: > 3x ULN, > 5x ULN, > 10x ULN, > 20x ULN
- Total bilirubin >2x ULN
- ALT or AST: > 3x ULN and Total bilirubin >2x ULN

Plots of ALT and AST vs. Total bilirubin by module will also be produced with reference lines at 3×ULN for ALT, AST, and 2×ULN for total bilirubin. In each plot, peak total bilirubin x ULN will be on the vertical axis and peak ALT or AST x ULN will be on the horizontal axis.

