5.	Received at least one regimen of prior systemic therapy and then experienced documented radiographic progression (for Substudy 1), and have no satisfactory treatment alternatives (for Substudy 2)
6.	Measurable disease by RECIST version 1.1 criteria
	ECOG performance status $\leq 1$ (Appendix 2)
8.	
 
Adequate organ functions as indicated by the following laboratory values (based on screening visit values from the central laboratory).
 
Hematological
 

	- Hemoglobin (Hgb) $\geq$ 9.0 g/dL
	
 
Absolute neutrophil count (ANC) ≥ <math>1.5 \times 10^9</math>/L
 
Platelet count ≥ <math>75 \times 10^9</math>/L
 

	- International normalized ratio (INR) 0.8 to upper limit of normal (ULN) or $\leq 3$ for patients receiving anticoagulant therapy such as warfarin or heparin
	• Hepatic
	- Total bilirubin $\leq 2 \times ULN$
	
 
Aspartate aminotransferase (AST) and alanine aminotransferase (ALT) ≤ 3 ULN (≤ 5 × ULN for patients with liver metastases)
 
Albumin ≥ 2.8 g/dL
 

	• Renal
	
 
Serum creatinine ≤ 1.5 × ULN, or
 
Creatinine clearance of ≥ 30 mL/min as estimated by the Cockcroft-Gault equation
 

 
9. Female and male patients of child-producing potential must agree to avoid becoming pregnant or impregnating a partner, respectively, during the study*, and for at least 120 days after the last dose of derazantinib.
 
Male patients are considered not to be of child-producing potential if they have azoospermia (whether due to vasectomy or an underlying medical condition). Female patients are considered not to be of child-producing potential if they are:
 
postmenopausal†, or
 
have had a hysterectomy and/or bilateral oophorectomy, bilateral salpingectomy or bilateral tubal ligation/occlusion, at least 6 weeks prior to screening, or
 
have a congenital or acquired condition that prevents childbearing.
 

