- 7. ECOG performance status  $\leq 1$  (Appendix 2).
- 8. Adequate organ functions as indicated by the following laboratory values (based on screening visit values from the central laboratory).
  - Hematological
    - Hemoglobin (Hgb)  $\geq$  9.0 g/dL
    - Absolute neutrophil count (ANC)  $\geq 1.5 \times 10^{9}/L$
    - Platelet count  $\geq 75 \times 10^9/L$
    - International normalized ratio (INR) 0.8 to upper limit of normal (ULN) or  $\leq 3$  for patients receiving anticoagulant therapy such as warfarin or heparin
  - Hepatic
    - Total bilirubin  $\leq 2 \times ULN$
    - Aspartate aminotransferase (AST) and alanine aminotransferase (ALT)  $\leq$  3 ULN ( $\leq$  5 × ULN for patients with liver metastases)
    - Albumin  $\geq 2.8 \text{ g/dL}$
  - Renal
    - Serum creatinine  $\leq 1.5 \times ULN$ , or
    - Creatinine clearance of  $\geq$  30 mL/min as estimated by the Cockcroft-Gault equation
- 9. Female and male patients of child-producing potential must agree to avoid becoming pregnant or impregnating a partner, respectively, during the study\*, and until at least 120 days after the last dose of derazantinib.

Male patients are considered not to be of child-producing potential if they have azoospermia (whether due to vasectomy or an underlying medical condition). Female patients are considered not to be of child-producing potential if they are:

- postmenopausal†, or
- have had a hysterectomy and/or bilateral oophorectomy, bilateral salpingectomy or bilateral tubal ligation/occlusion, at least 6 weeks prior to screening, or
- have a congenital or acquired condition that prevents childbearing.

Male or female patients of child-producing potential must agree to comply with one of the following until at least 120 days after the last dose of derazantinib:

a) Abstinence from heterosexual activity‡

\* From the day of first study medication, or for oral contraception from 14 days before first study medication.

\* Postmenopausal is defined as at least 12 months with no menses without an alternative medical cause; in women < 45 years of age a high follicle stimulating hormone (FSH) level in the postmenopausal range may be used to confirm a post -menopausal state in women not using hormonal contraception or hormonal replacement therapy. In the absence of 12 months of amenorrhea, a single FSH measurement is not sufficient.

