# 6.5 Clinical laboratory tests

Safety laboratory determinations will include hematology, blood chemistry, liver function tests, and coagulation tests at the Screening visit (within 1 week prior to dosing), Cycle 1 Days 1 and 15, Day 1 of all subsequent cycles, the End of Treatment visit, and the 30-day Safety Follow-up visit. If clinically indicated, some or all of these tests may be repeated on other study days. All laboratory tests will be performed at a central laboratory designated by the Sponsor.

- Hematology: complete blood count (CBC) including hemoglobin, hematocrit, white blood cell count (WBC) with 5-part differential, red blood cell (RBC) count, and platelet count
- Blood chemistry: albumin, bicarbonate, blood urea nitrogen (BUN), calcium, chloride, creatinine, glucose, magnesium, phosphate, potassium, total protein, sodium, and uric acid
  - Creatinine clearance as calculated by the Cockcroft-Gault equation (at the Screening visit only)
  - 25-hydroxy vitamin D and 1,25-dihydroxy vitamin D (at C1D1, C3D1, C5D1, and the End of Treatment visit only),

- Liver function tests (LFT): ALT, AST, ALP, total and direct bilirubin, lactate dehydrogenase (LDH)
- Coagulation tests: prothrombin time (PT), INR, and partial prothrombin time (PTT) (at the Screening and End of Treatment visits and if clinically indicated)
- Serum pregnancy test: for women of child-producing potential at the Screening visit (within 72 hours prior to dosing), and End of Treatment visit. In addition, serum- or urine pregnancy testing will be performed monthly (on Day 1 of each treatment cycle) while the patient receives study treatment, at the 30-day Safety Follow-up visit, and monthly until 120 days after the last administration of study drug. Pregnancy testing after the End of Treatment may be performed at the patient's local gynecologist to reduce the burden related to study visits at the site, but must be communicated to the study investigator.

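### The Hy's law rule has no time link, ALP split or baseline-relative term, so in this biliary cancer it can count cholestasis as Hy's law cases

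*SAP*

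**What the plan says.** SAP section 3.2.8.2, under Hy's law, covers patients with raised ALT, AST and "total bilirubin post baseline will be summarized descriptively as follows and Hy's law cases identified". Three sets of thresholds follow: ALT and AST above 3, 5, 10 and 20 × ULN; total bilirubin above 2 × ULN; and the combination, "ALT or AST: > 3x ULN and Total bilirubin >2x ULN". The SAP gives no other definition of a case.

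On the plots it says "In each plot, peak total bilirubin x ULN will be on the vertical axis"; the other axis carries the patient's highest transaminase value. Nothing ties the dates of the two peaks together.

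Inclusion criterion 8 (Protocol section 4.2 and synopsis) caps total bilirubin at 2 × ULN for everyone. It caps AST and ALT at 3 × ULN, but at "≤ 5 × ULN for patients with liver metastases". Protocol section 6.5 lists the liver tests as "ALT, AST, ALP, total and direct bilirubin, lactate dehydrogenase (LDH"), drawn at screening, Cycle 1 Days 1 and 15, Day 1 of every later cycle, End of Treatment and the 30-day follow-up.

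**The concern.** A Hy's law table is read as evidence of drug-induced hepatocellular injury. In a cancer of the bile ducts, bilirubin and transaminases can also rise because a duct or stent is blocked. The protocol recognises this setting: section 1 describes background biliary tract or liver disease as frequent, and the QLQ-BIL21 questionnaire asks about jaundice and drainage tubes. Exclusion criterion 7 removes active or unresolved hepatobiliary disorders at entry but cannot prevent later obstruction.

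The liver result matters here. Protocol section 7.8 names increased transaminases as an important identified risk, the only risk it places in that class. Section 1.5.3 reports that the three dose-limiting toxicities in the earlier Phase 1/2 study were all Grade 3 AST increases. The present trial has one arm, so no control group shows how many flags the disease produces by itself. A raw count could therefore be credited to the drug.

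**Working it through.** The plan states no expected number of Hy's law cases, so there is no figure to reproduce. The check compares entry limits with screen thresholds and then illustrates the effect of pairing.

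**Step 1. Can a patient meet the rule on screening values?** Entry limits are from Protocol section 4.2, thresholds from SAP section 3.2.8.2.

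| Test | Entry limit (× ULN) | Screen (× ULN) | Can exceed at entry? |
|---|---|---|---|
| AST/ALT, liver metastases | 5 | > 3 | Yes |
| AST/ALT, others | 3 | > 3 | No |
| Total bilirubin, all | 2 | > 2 | No |

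Only the transaminase half can be met at entry, and only by patients with liver metastases. A bilirubin rise is always needed to complete the rule.

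**Step 2. How large a bilirubin rise?** The relative rise needed to reach 2 × ULN is 2/b − 1 for a baseline of b × ULN; the rule is met just above that.

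- b = 1.0: 2/1.0 − 1 = 100%
- b = 1.5: 2/1.5 − 1 = 33%
- b = 1.9: 2/1.9 − 1 = about 5%
- b = 2.0: any rise

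**Step 3. Effect of pairing, on assumed rates.** Let V be the number of post-baseline draws, and let p be the per-visit probability of ALT/AST above 3 × ULN and, separately, of bilirubin above 2 × ULN. Assume independence between tests and visits. Neither p nor V comes from the documents, although the Protocol expects most patients to be treated for 1 to 8 months.

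- Peaks paired at any time: [1 − (1 − p)^V]²
- Same visit: 1 − (1 − p²)^V
- Patient always above 3 × ULN on ALT/AST: 1 − (1 − p)^V

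For V = 6 and p = 0.05: 1 − 0.95^6 = 0.265; squared, 0.070; same visit, 1 − 0.9975^6 = 0.015.

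| V | p | Peaks, per 100 | Same visit, per 100 | Stable above 3 × ULN, per 100 such patients |
|---|---|---|---|---|
| 3 | 0.03 | 0.8 | 0.3 | 8.7 |
| 3 | 0.05 | 2.0 | 0.7 | 14.3 |
| 3 | 0.10 | 7.3 | 3.0 | 27.1 |
| 6 | 0.03 | 2.8 | 0.5 | 16.7 |
| 6 | 0.05 | 7.0 | 1.5 | 26.5 |
| 6 | 0.10 | 22.0 | 5.9 | 46.9 |
| 9 | 0.03 | 5.7 | 0.8 | 24.0 |
| 9 | 0.05 | 13.7 | 2.2 | 37.0 |
| 9 | 0.10 | 37.5 | 8.6 | 61.3 |

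The two tests are probably positively correlated, which would narrow the gap between the peak and same-visit columns.

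**Step 4. What a time link cannot do.** If ALT/AST is above 3 × ULN at every visit, same-visit pairing gives 1 − (1 − 1 × p)^V, which is the last column again. A time window removes chance pairings of distant peaks but does nothing for stable pre-existing elevations. Those need the baseline multiple and the ALP split. The effect of an ALP split cannot be computed from the documents.

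**The case against.** The strongest reply is that this is a broad descriptive screen that over-includes rather than hides cases and drives no test or stopping rule. Much of the missing context also appears elsewhere. Section 3.2.8.2 plans shift tables from baseline and by-patient listings with change from baseline. Investigators judge causality for each adverse event and may attribute it to the disease under study (Protocol section 8.7). The Medical Monitor evaluates all serious events (section 8.4), the DMC reviews safety, and transaminase elevations are tabulated as events of special interest. Neither document defines Hy's law or sets an ALP cut-off, so nothing in the plan is contradicted.

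All of this is accurate, and it rules out several stronger readings:

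- *Pre-existing elevations alone will be labelled as cases.* They cannot be. Eligibility is judged on screening values, where bilirubin may not exceed 2 × ULN.
- *Any patient may enter at 4 × ULN.* That applies only with liver metastases, a subset whose size is not given.
- *The plan ignores baseline.* Only the Hy's law rule does; it counts post-baseline values without relating them to baseline.
- *There is no individual review.* General causality and serious-event review exist; a review specific to Hy's law cases is not described.
- *The table row pairs unrelated dates by rule.* Only the plots are stated to use peaks. On timing the row is silent.

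The reply does not repair the combined row. As far as the SAP describes them, the shift tables do not link ALT, bilirubin and ALP within a patient. Listings leave the reader to reconstruct cases by hand. The same SAP does set categories of change from baseline for QTc (section 3.2.8.4), so baseline-relative reporting is already its practice.

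**Conclusion.** The point holds as a reporting weakness. The combined rule can count cholestasis as Hy's law cases; it should not be said that it will. The documents do not establish that a given number of false cases will appear, because they give no rates of obstruction or of raised liver tests, and the SAP does not say outright that meeting the third threshold set is by itself a case.

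The firm findings are the limits in Step 1: the transaminase half can be met with no change on treatment in patients with liver metastases, and the bilirubin rise then needed can be as small as about 5% from 1.9 × ULN. The rates in Step 3 are illustrative and rest on assumed, independent per-visit probabilities. The ALP argument rests on the general meaning of Hy's law, not on an inconsistency in the plan.

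This is a free improvement to a descriptive safety analysis. It affects no primary endpoint, alpha, power or sample size.

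**What to change.** Amend the Hy's law paragraph of SAP section 3.2.8.2 as follows:

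1. Call patients who meet the thresholds potential Hy's law cases.
2. Require the two elevations on the same date or within a stated window (for example 30 days).
3. Keep every flagged patient, but split the combined row by ALP at a cut-off the sponsor states (for example below 2 × ULN against 2 × ULN or above).
4. For patients with ALT, AST or bilirubin above ULN at baseline, add multiples of baseline.
5. List flagged patients with dated ALT, AST, total and direct bilirubin and ALP.

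The window and the ALP cut-off are proposals; the sponsor should choose and state its own. The cost is a few SAP lines, some table rows and one listing. ALP and direct bilirubin are already collected with the liver tests, so no new data are needed.

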# 3.2.8.3 Vital Sign Variables

Values and change from baseline for vital signs, including systolic blood pressure, diastolic blood pressure, heart rate, respiratory rate, body temperature, and weight will be summarized by scheduled time of evaluation. Repeated or unscheduled tests will not be summarized for each scheduled visit.

By patient listings for all vital signs will also be presented.

# 3.2.8.4 Electrocardiogram (ECG)

The actual value and change from baseline to each visit and at end of study will be descriptively summarized by visit for ECG parameters (e.g., heart rate, RR interval, PR interval, QRS duration, QT interval, QTcF interval and QTcB interval). For all patients, a standard, triplicate, 12-lead ECG must be performed at all study visits using the pre-programmed device provided by the Sponsor. Summary tables will consider the mean of the triplicate measurements at each visit as the single reported value.

A categorical analysis of QTcF interval and QTcB interval correction will also be presented, based on the number and percentage of patients meeting or exceeding specific thresholds for absolute QTcF/QTcB interval prolongation and change from baseline in QTcF/QTcB interval. In this analysis, the mean of the triplicate measurements will not be used; instead, the maximum at each timepoint will be considered.

For absolute QTcF/QTcB interval prolongation, the number and percentage of patients within the following thresholds will be summarized at each visit. The worst (largest) value will also be summarized.

- Interval  $\leq 450 \text{ ms}$
- Interval >450 ms and  $\leq$ 480 ms
- Interval >480 ms and  $\leq$ 500 ms
- Interval >500 ms

The change from baseline in QTcF/QTcB interval to the worst (largest) post-baseline observation and at each study visit will also be summarized, considering the following thresholds:

- Interval increased from baseline  $\leq 30 \text{ ms}$
- Interval increased from baseline >30ms and  $\leq 60$  ms
- Interval increased from baseline >60 ms

For the analysis of change from baseline, the mean of the triplicate measurements will be used for baseline, but the maximum of triplicate measurements will be used for post-baseline values.

Local and central ECG data will be presented separately in the summary tables, and will be presented by timepoint. All ECG data will be provided in a by-patient listing.

#### 3.2.8.5 ECOG

ECOG performance status will be summarized in a shift table, which will summarize values at baseline, each visit and the maximum values during the study.

All ECOG performance assessments will be provided in a by-patient listing.

#### 3.2.8.6 Other Safety Variables

By patient listings for physical examination, eye examination, and pregnancy test will be presented.

# 4 CHANGES FROM PLANNED ANALYSIS

- The protocol indicates the primary analysis population is restricted to FISH performed by a central laboratory. However, this was not the case and therefore reference to central FISH has been removed
- Safety/ITT Population has been updated from "All patients who receive any amount of study drug" to 2 separate definitions for each substudy to take into consideration the substudy that each patient was enrolled in:
  - The Safety/ITT population for Substudy 1 will include all patients with locally or centrally confirmed *FGFR2* fusions/rearrangements who receive any amount of study drug.
  - The Safety/ITT population for Substudy 2 will include all patients with locally confirmed *FGFR2* mutations or amplifications who receive any amount of study drug.
- The mITT population definition was updated from "All patients who receive any amount of study drug and have at least one post-baseline disease assessment." to "All patients in the Safety/ITT population, and have at least one post-baseline disease assessment (at least one post-baseline imaging assessment in accordance with RECIST 1.1, or documented clinical progression [every effort should be made to objectively assess radiographic progression]). Patients who have primary reason for discontinuation as death will be included in the mITT population."
- The PP population was updated from "All patients in the mITT Population who have no major protocol violations during the study, receive at least one cycle (28 doses) of ARQ 087, have at least one post-baseline efficacy measurement, and test positive for FGFR2 gene fusion by the central laboratory" to "will include all patients in the mITT population who have no important protocol (IPD) deviations which are determined to potentially impact efficacy analyses during the study. Protocol deviations will be identified prior to final analysis." This was to reflect the Labcorp standard to use "important" rather than "major", and furthermore to allow flexibility in defining those IPDs that may affect the efficacy endpoints.
- DCR has been added as an exploratory efficacy endpoint, and is defined as the achievement of confirmed CR or PR or SD (or Non-CR/Non-PD for patients with non-measurable disease).
- The minimum duration of SD in the protocol had referenced both 8 weeks (+/-2 days) on page 101 and 8 weeks (+/- 3 days) on page 105 of the protocol. Following client discussion, it was decided that the minimum duration of SD should instead be at least 6 weeks i.e. 42 days as per RECIST guidelines. This minimum duration will also apply to Non-CR/Non-PD.
- Although RECIST does not expect the best overall response to include non-CR/non-PD (NN) for non-measurable disease, in the event that this happens it will be treated as its only entity and in terms of hierarchy it will fall between SD and PD.
- Exploratory endpoints have been added to take into consideration of investigator assessments for ORR, PFS and DCR.

